ISOC MMPNA Block Group (n=80 TKA and 80 THA patients) will receive the ISOC 4-drug MMPNA nerve blocks at the L2-L4 and L4-S3 nerves/plexi. These blocks will be placed before the administration of spinal anesthesia, per our ISOC.

Active Control Block Group (n=20 TKA and 20 THA patients) will receive “active control” nerve blocks comprised of plain bupivacaine. As with the ISOC MMPNA Block Group, these blocks will be placed before the administration of spinal anesthesia, per our ISOC. Again, these blocks will involve the same L2-L4 and L4-S3 nerves/plexi as those for the ISOC MMPNA Block Group.

All study team members will be blinded to the nerve block treatment group/drug the patient receives/received for the described blocks. The only unblinded person regarding the study treatment will be the anesthesia team member who prepares the nerve block injection syringes, based on the randomization envelope assignment. This person who prepares the drug syringes will be otherwise uninvolved with the care of the study patient.

Table 1. Anatomic location of the analgesic nerve blocks used based on TKA versus THA

Basic description of regional anesthesia and analgesia care plan	TKA block details	THA details
Spinal anesthesia, L2-L4 and L4-S3 perineural/plexus single-injection nerve blocks	L2-L4 nerve block entails the femoral nerve in the groin. The L4-S3 nerve block entails the sciatic nerve as it emerges from the sciatic notch deep to the gluteal musculature.	L2-L4 plexus block entails the lumbar plexus within the psoas compartment, 2-3 inches lateral to the lumbar spine midline. The L4-S3 plexus block entails the lumbosacral trunk and parasacral plexus, which lies lateral to the lateral margin of the proximal sacrum. The plexus lies deep to the sacroiliac ligament.

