5.0 Statistical Analysis

5.1 Analysis Plan

Data will first be assessed for outliers (+/- 2 SD from the mean) and normality. Outliers will be corrected, if possible, or dropped from the analyses. Distribution, measures of central tendency, variability, and normality will be examined. Data transformations or non-parametric techniques will be applied as needed. We will delete observations with missing values. Spearman correlation coefficients will be computed to examine associations between nerve block drug treatments, replacement surgery

type (hip versus knee), and the outcome measures (SF-MPQ, SF-8, SF- 36, WOMAC, FIM, repeated chair stand test, Opioid Symptom Distress Scale, Defense and Veterans Pain Rating Scale and its Supplemental Questions) from all time points (1 day, 2 day, 3 day, 4 day, Follow-Up Visit 1, Follow-Up Visit 2). Associations between the outcomes across time points will also be examined with Pearson (SF-MPQ, SF-8, SF-36, WOMAC, repeated chair stand test, Opioid Symptom Distress Scale) and Spearman (FIM, Defense and Veterans Pain Rating Scale and its Supplemental Questions) correlation coefficients. We will test all hypotheses and aims by conducting longitudinal multi-level modeling. The level-one unit will be the repeated measures across time, the level-two unit will be the individual patient, and the level-three unit will be nerve block type and surgical site (knee versus hip) groupings (with additional analyses involving age and diabetes status, reflecting the randomization strata). This mixed model procedure will allow the assessment of outcome and exposure variables relationships while adjusting for covariates, and separate assessments of fixed and random effects (i.e., group and individual-level data) using highly correlated repeated measures data. Covariates included in modeling will be age, diabetes status, gender, weight, smoking status, initial health status (e.g., baseline SF-8 / SF-36 and WOMAC), and concurrent general health status (e.g., daily SF-8, subsequent SF-36, and WOMAC).

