The study drug is administered only once, at the time of the nerve block before surgery. So no adverse event would involve “continuous receipt of study drugs.”

We do not anticipate any withdrawn participants from the study, with the exception of those for which the anesthetic care plan was converted to GETA. This is because (i) the nerve blocks and/or spinal failed, or (ii) that the nerve blocks and/or spinal were appropriate for the “typical” surgical procedure. In further detail, the particular surgical procedure that was forced to a GETA anesthetic plan was likely atypically lengthy or complex, rendering the study case as likely not comparable to other enrolled/completed study participants. Therefore, we do not anticipate any further data collection as being representative of a scientifically meaningful “intent-to-treat.”

The basis of adverse event severity related to the study entails 1) association with the investigational drug or study treatment(s); 2) serious nature of the adverse event; and 3) unexpected nature of the adverse event. The nerve block drug involved in the active control group (bupivacaine) to which the experimental group drugs are added (clonidine-buprenorphine-dexamethasone) are not expected to create untoward surgical events and/or blood loss complications since none of these drugs alter physiologic coagulation. It is not anticipated that surgical complications that entail blood loss, of whatever severity, will be traceable to the nerve block treatment group. However, we will still record and grade estimated blood loss of the surgical procedure (<500 mL, 500-1L, > 1L) and determine any potential associations with nerve block treatment group.

Subjects withdrawn from study participation due to an adverse event will be replaced.

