APPENDIX 1: Study Calendar

	Screening Visit ^a	Baseline Visit	Day of surgery		Post-Op Day 1	Post-Op Day 2	Post-Op Day 3	Post-Op Day 4	Post-Op Day 5	Follow-Up Visit 1 ^d	Follow-Up Visit 2 ^{c, e}
			Pre-Procedure	Post-Procedure							
Clinical Assessments											
Informed Consent	X										
Determine Eligibility	X										
Demographics	X										
Orthopedic & IMPACT evaluation		X									
Crude Sensation in L2-L4 & L4-S3		X			X	X	X	X	X		X
Straight Leg Raise & Range of Motion		X			X	X	X	X	X		X
Functional Independent Measure (FIM)		X			X	X	X	X	X		X
Standing Balance Test		X			X	X	X	X	X		X
Single Leg Balance Test ^g		X									X
Gait Speed		X			X	X	X	X	X		X
Repeated Chair Stand Test		X				X	X	X	X		X
Stair Climbing Time		X									X
Physical Therapy/ Therapeutic Exercises					X	X	X	X	X		
Comorbidity (CIRS)		X									
Interim Changes											X
Discharge Disposition											X
Opioid Consumption					X ^g						
Anesthesia/Study Drugs			X								
Adverse Events		X	X	X	X	X					
Concomitant Medications		X	X	X	X	X					

	Screening Visit	Baseline Visit	Day of surgery		Post-Op Day 1	Post-Op Day 2	Post-Op Day 3	Post-Op Day 4	Post-Op Day 5	Follow-Up Visit 1	Follow-Up Visit 2 ^{c, e}
			Pre-Procedure	Post-procedure							
Questionnaires											
SFMPQ-2 ^b		X	X	X	X	X	X	X	X		X
DVPRS		X	X	X						X	X
DVPRS- in hospital ^b					X	X	X	X	X		
ORSDS ^b		X			X	X	X	X	X		
QOR-15 ^b		X			X	X	X	X	X		X
WOMAC		X									X
SF-8 ^b			X		X	X	X	X	X	X	
SF-36		X									X
Falls Questionnaire		X			X	X	X	X	X		X

a. The screening visit and baseline visit can be completed on the same day.

b. On post-op hospital days and post-op week 6 follow-up visits, these questionnaires will be completed before the subject has their first physical therapy session for the day.

c. If a patient decides to withdraw from the study after having their surgery, or is withdrawn by the study team during or after their surgery, they will be asked to complete Follow-Up Visit 2.

d. Follow-up visit 1 will occur with the patient's already scheduled standard of care follow-up orthopedic visits. Follow-Up Visit 1 may be performed as a phone call if necessary.

e. Follow up visit 2 will be scheduled to coincide with the patient's standard of care follow-up orthopedic visits.

f. Patient must pass the standing balance test first, before the single leg balance test can be attempted.

g. Opioid consumption will stop being collected at the time of the patient's discharge.

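### Patients converted to general anesthesia after the randomised block may be withdrawn without a 24 h pain score, and no analysis population says whether they count

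*Combined protocol and SAP*

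**What the plan says.** Section 4.1 states that the randomised "blocks will be placed before the administration of spinal anesthesia, per our ISOC". Section 9.3, under the heading on withdrawal of subjects due to adverse events, adds that the study drug is given once, before surgery.

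The same part of Section 9.3 expects no withdrawals "with the exception of those for which the anesthetic care plan was converted to GETA". One cause it gives for conversion is that "the nerve blocks and/or spinal failed"; the other is unusually long or complex surgery. It continues: "Therefore, we do not anticipate any further data collection as being representative of a scientifically meaningful" intent-to-treat. This is the only mention of intent-to-treat in the documents. The section closes with: "Subjects withdrawn from study participation due to an adverse event will be replaced".

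Appendix 1, footnote c, covers a patient who withdraws after surgery or "is withdrawn by the study team during or after their surgery, they will be asked to complete Follow-Up Visit 2". It names no other visit.

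Sections 4.4 and 5.1 make SF-MPQ-2 pain at 24 h the primary outcome, tested in a mixed model in which "The level-one unit will be the repeated measures across time". Section 5.1 also states: "We will delete observations with missing values". No part of Section 5 says which randomised patients enter the primary analysis.

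**The concern.** Conversion to general anesthesia happens after randomisation and after the single dose of study drug. Removing patients on a post-treatment event protects the comparison only if removal is unrelated to arm or unrelated to pain. One stated cause of conversion is failure of the block, which is the randomised treatment, so independence cannot be taken for granted.

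If conversion differs by arm and converted patients would have had different pain at 24 h, the groups compared at 24 h are no longer those that were randomised. A score that nobody asked for on Day 1 cannot be restored at analysis. The plan also does not require conversions to be reported by arm, so a reader could not judge how much this matters.

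**Working it through.** **Patient flow.**

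| Step | Source | Consequence |
|---|---|---|
| Block given before spinal and surgery | 4.1, 9.3 | Conversion is a post-treatment event |
| Conversions are the one anticipated class of withdrawal | 9.3 | Worded as an expectation, but the only guidance for these patients |
| Follow-Up Visit 2 requested after withdrawal | Appendix 1, footnote c | The 24 h score is neither requested nor forbidden |
| Missing observations deleted; no population named | 5.1 | No 24 h value from these patients in the primary comparison |

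**Figures in the documents.** No conversion rate and no SF-MPQ-2 SD are given. The only loss figure is the attrition allowance in Section 5.6: 6/20 = 0.30 control and 24/80 = 0.30 MMPNA. The power figures there concern block duration, not pain scores, and do not bear on this point.

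**Size of the shift.** Let pC and pM be the shares removed from control and MMPNA. Let k be the excess 24 h pain of removed over retained patients, in SD, the same in both arms. Each retained mean is the full-arm mean minus p × k, so the control-minus-MMPNA difference moves by

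shift = k × (pM − pC).

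A positive shift overstates the MMPNA benefit. The 30% allowance gives k × (0.30 − 0.30) = 0. The rates below are assumptions, with k = 1. The last two columns give the chance of a false rejection with no true difference in the full sample. They come from the noncentral t distribution on the retained patients, two-sided 0.05, and are written pooled (40 vs 160) / per procedure (20 vs 80).

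| Control vs MMPNA removed | Shift (SD) | Favouring MMPNA | Favouring control |
|---|---|---|---|
| Equal | 0 | 2.5% / 2.5% | 2.5% / 2.5% |
| 5% vs 3% | −0.02 | 1.9% / 2.1% | 3.2% / 3.0% |
| 10% vs 3% | −0.07 | 1.0% / 1.3% | 5.7% / 4.5% |
| 20% vs 5% | −0.15 | 0.3% / 0.6% | 11.7% / 7.8% |
| 3% vs 10% | +0.07 | 5.8% / 4.6% | 1.0% / 1.3% |

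At 10% vs 3%, k = 0.5 gives −0.035 and k = 1.5 gives −0.105.

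**Scale.** The difference detectable with 80% power is 0.498 SD pooled and 0.707 SD per procedure. A shift of 0.07 SD is 0.07/0.498 = 14% and 0.07/0.707 = 10% of these.

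**What the mixed model could recover.** Appendix 1 schedules the SF-MPQ-2 at baseline and pre-procedure, and Follow-Up Visit 2 is requested, so three other rows may exist. Assume compound symmetry with correlation r and arm-by-time means. The slope of the 24 h score on the mean of those rows is b = 3r/(1 + 2r). If a share m of the excess pain is also present at those visits, the share of the shift that remains is 1 − b × m.

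- r = 0.4: b = 1.2/1.8 = 0.667.
- m = 0: share left 1.00, so 0.07 stays 0.070.
- m = 0.4: share left 0.73, so 0.07 becomes 0.051.
- m = 1: share left 0.33, so 0.07 becomes 0.023.
- At m = 1, r = 0.2 leaves 0.57 and r = 0.6 leaves 0.18.

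A simulation of 4,000 runs at 3% vs 10% gave 0.069, 0.051 and 0.024 for the three values of m. The model therefore recovers nothing if the extra pain is confined to 24 h.

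**The case against.** The strongest reply is that conversion should hardly depend on arm. The spinal provides the surgical anesthesia and the blocks are for pain afterwards (Sections 2.1 and 2.2). Both arms receive the same bupivacaine within each diabetes stratum (3.6) and the same standardised spinal (4.1), and the study team is blinded. This stands: a large difference is unlikely, and 20% vs 5% should be read only as an outer case. It does not settle the matter, because Section 9.3 itself lists block failure as a cause and no rate is given.

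The likelier direction is also conservative. Losing more high-pain controls understates the MMPNA benefit; overstatement needs more removal in the MMPNA arm, for which the documents give no reason. That stands too, but a bias against the tested treatment is still a bias.

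Avoiding general anesthesia as a confounder is a stated aim (Sections 2.1, 2.3, 4.1), and Section 9.3 discloses its reasoning in advance. This justifies an analysis without conversions. As the primary analysis, it relies on conversion being alike in both arms, and the argument from atypical surgery does not cover failed blocks.

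The deletion rule can be read as dropping a row rather than a patient, and footnote c does not cancel the Day 1 questionnaire. Both readings are fair, but neither produces a 24 h score that was not requested. The 30% attrition allowance covers power, not comparability.

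**Conclusion.** The concern holds and should be fixed. Followed as written, the plan can leave randomised, treated patients without the primary outcome on account of a post-treatment event, and it does not say whether they belong to the analysis.

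The gap is clear from the text, but its effect is uncertain and probably small. It is zero if removal is alike in both arms, 0.02 SD at 5% vs 3% and 0.07 SD at 10% vs 3%. All non-zero figures rest on assumed conversion rates and an assumed 1 SD excess of pain in removed patients. The recovery figures also rest on an assumed correlation. With 20 controls per procedure, each control conversion removes 1/20 = 5% of that arm, so a few cases are enough to create an imbalance.

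Replacement after an adverse event is a lesser matter. Under Section 4.2 the replacement already takes the next randomised envelope, so the only open question is whether the replaced patient's data are kept.

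**What to change.** - Define the primary population in Section 5 as all randomised patients who received the study block, analysed in the assigned arm, including conversions to general anesthesia and adverse-event withdrawals. Limiting it to patients who received the block is acceptable because treatment is a single blinded dose.
- Request the 24 h SF-MPQ-2 from these patients where they are able and consent, and reconcile Section 9.3 with Appendix 1, footnote c.
- State that the mixed model keeps all available rows of a patient whose 24 h score is missing.
- State that a replaced patient's data stay in the analysis.
- Report conversions and withdrawals by arm and procedure.
- Keep the analysis excluding conversions as a sensitivity analysis.

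The cost is a small protocol amendment, a few sentences in the analysis plan and a few extra in-hospital questionnaires. The downside is slightly noisier primary data from atypical surgical cases. Clinical management does not change.

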events in both groups with specific focus on those deemed definitely, probably, or possibly related to interventions. For adverse events, clinical judgments will be considered more important than statistical testing.

Prolonged analgesic duration Sustained / prolonged nerve block analgesia, which we hypothesize to be true in our ISOC MMPNA Group, is NOT a complication that warrants medical attention as a possible complication. That this is NOT a complication is especially true in the context of perineural analgesia being designed to facilitate postoperative physical therapy in the first few days after surgery. In our evaluation of analgesic duration, a central question for patients will be “when did you first take a prescription opioid pain pill, but it did not help?” Another (indicating even further pain severity) is “when did you first get an intravenous opioid dose, but it did not help? The dates and times of these events are important and clinically practical indicators that the perineural analgesia is no longer effective. This is because postoperative oral multimodal analgesia is designed to (i) supplement the lingering analgesic effects of the nerve block, and (ii) delay the onset of the peak pain score encountered after the perineural analgesia “wears off.” “Peak rebound pain scores” may not necessarily entail excruciating pain. But if excruciating pain is encountered despite oral and intravenous opioids, then it is likely that there is no persisting perineural analgesia. Conceptually, when combining CBD with bupivacaine (in the ISOC MMPNA group), the bupivacaine provides short-lived numbness and analgesia (e.g., a theoretical 12-16 hr), but the CBD likely sustains perineural analgesia without numbness (e.g., for an additional theoretical 24 hr). The study is designed to accurately capture these two separate phases of analgesia, since we do not have preliminary data on these separate phenomena (analgesia with numbness, then analgesia without numbness).

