5.6 Sample Size Determination

Although the SF-MPQ data is the basis of our specific aim, we do not have our own preliminary SF-MPQ data. So we will base our sample size on our most robust data, that being nerve block duration from our observational data (40 hr mean, with 14 hr standard deviation). Hip replacement and knee replacement surgery are different procedures requiring anatomically different nerve blocks as described above, so we will consider these samples as separate. We consider a doubling of the nerve block duration (15 hr for plain bupivacaine, 30 hr for bupivacaine-CBD) as a clinically significant difference with respect to the military objectives of evacuation and transport. We forecast that as a single-drug (and based on historical literature), the standard deviation of plain bupivacaine duration would be half of the 15 hr projected duration (i.e., 7.5 hr). Due to likely variability in study participant responsiveness to the 4-drug mixture, we predict that the standard deviation of the bupivacaine-CBD treatment would also be half of the projected 30 hr duration (i.e., 15 hr). We believe that the 30 (SD=15) hr duration for bupivacaine-CBD is a reasonably conservative duration based on our preliminary data of 40 (14) hr block duration. Using a 2-tailed t-test with $\alpha=0.05$, 20 patients per procedure for bupivacaine treatment, and 80 patients per bupivacaine-CBD treatment would yield 95% statistical power. This sample size will also accommodate for our multiple secondary aims. Attrition of 6 active control treatment patients ($n=14$) and of 24 MMPNA-treated patients ($n=56$) will still yield just over 80% statistical power. All calculations were performed using IBM SPSS SamplePower version 3.0.1, Chicago, IL.

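### Estimated blood loss is related to nerve block group only through three grades; comparing the volume in mL would be a cheap improvement to a minor safety check

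*Combined protocol and SAP*

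**What the plan says.** Section 9.3, under the sub-heading on withdrawal because of adverse events, first states the expectation: "It is not anticipated that surgical complications that entail blood loss, of whatever severity, will be traceable to the nerve block treatment group". It then adds a check against the allocated block drugs: "we will still record and grade estimated blood loss of the surgical procedure (<500 mL, 500-1L, > 1L) and determine any potential associations". No test, effect size, distribution or power is given, and no reason for the two cut points.

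Blood loss does not appear among the aims (Section 1.0), the further metrics in Section 4.1, the outcomes in Sections 4.4 and 5.1, or the study calendar in Appendix 1. No other section therefore supplies an analysis in mL.

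The arm sizes are in Section 4.1: "ISOC MMPNA Block Group (n=80 TKA and 80 THA patients") and "Active Control Block Group (n=20 TKA and 20 THA patients"). On knee and hip replacement, Section 5.6 says "so we will consider these samples as separate". For adverse events, Section 5.2 says that "clinical judgments will be considered more important than statistical testing".

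**The concern.** A grade is a coarsened volume. Whoever assigns it has already judged how many mL were lost, so comparing grades discards information that was available at no cost. A difference between arms that stays inside one band cannot be seen. If most operations fall in the lowest band, the comparison depends on the few patients above it, and the control arm has only 40 patients, or 20 per procedure.

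The check exists to test the protocol's own expectation that blood loss will not be related to the block drugs. A finding of no association on three grades would seem to support that expectation, yet it could miss a difference that the volumes would have shown.

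**Working it through.** **1. The plan's own figure.** There is none to reproduce. The only power statement (Section 5.6) concerns block duration and has no bearing on blood loss.

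**2. Inputs from the documents.** Cut points are 500 mL and 1 L. Controls: 20 + 20 = 40. Four-drug arm: 80 + 80 = 160.

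**3. Inputs that are assumed.** Blood loss is log-normal, with median 150 to 800 mL and log-SD σ from 0.4 to 0.8, rounded to 50 mL. Tests are two-sided at 0.05.

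**4. Shift giving 80% power on the log scale.** δ = (1.96 + 0.84) × σ × √(1/n₁ + 1/n₂).
- 40 vs 160: √(1/40 + 1/160) = 0.177, so δ = 0.50σ.
- 20 vs 80: √(1/20 + 1/80) = 0.25, so δ = 0.70σ.

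In mL, the shift in the median is median × (e^δ − 1). At 40 vs 160:
- median 150, σ 0.4: 150 × (e^0.198 − 1) ≈ 33 mL
- median 250, σ 0.6: 250 × (e^0.297 − 1) ≈ 86 mL
- median 400, σ 0.6: 400 × (e^0.297 − 1) ≈ 138 mL

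**5. Large-sample check without simulation.** For a normal variable cut into three bands with probabilities Pᵢ and cut points cᵢ, the retained efficiency is e = Σ(φ(cᵢ₋₁) − φ(cᵢ))²/Pᵢ. Power on the grades is Φ(2.80√e − 1.96), against 80% on the continuous value.

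| Below 500 mL | Above 1 L | e | Power on grades | Loss (points) |
|---|---|---|---|---|
| 27% | 27% (best placed) | 0.81 | 71% | 9 |
| 50% | 10% | 0.75 | 68% | 12 |
| 70% | 5% | 0.62 | 60% | 20 |
| 80% | 3% | 0.52 | 52% | 28 |
| 90% | 1% | 0.35 | 38% | 42 |
| 95% | 0.5% | 0.23 | 27% | 53 |

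Worked row: √0.23 = 0.48; 2.80 × 0.48 − 1.96 = −0.62; Φ(−0.62) = 27%.

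**6. Simulation.** A rank-sum test on mL was compared with the same test on the three grades. The share below 500 mL in the unshifted arm is Φ(ln(500/median)/σ). With the control arm raised, 40 vs 160:

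| Median, σ | Share below 500 mL | Shift | Loss (points) |
|---|---|---|---|
| 150 mL, 0.4 | 99.9% | 33 mL | 53 |
| 250 mL, 0.6 | 88% | 86 mL | 21 |
| 400 mL, 0.6 | 64% | 138 mL | 11 |

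Over the whole grid and both arm sizes, the loss is about 7 to 55 points when controls bleed more.

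When the four-drug arm bleeds more, it is about 6 to 78 points. With that arm held at the stated median and controls lower, median 250 mL and σ 0.6 gives 76% power on mL and 25% on grades. Median 400 mL and σ 0.6 gives 77% and 54%.

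The upper ends move by a few points with the placement of the shift and with the reference test: 80% for the log-scale test, about 75-78% for the rank test on mL.

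**7. Larger shifts.** With a shift giving 99% power on the log scale (controls higher, 40 vs 160), the loss runs from 2 to 59 points. It is 5 points or less in every case with a median of 400 mL or more.

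**The case against.** The strongest reply is that the protocol asks about complications. The sentence sits with adverse events and concerns blood loss of differing severity. Grading is a natural scale for that, and Section 5.2 ranks clinical judgment above testing. The largest power losses also belong to shifts of tens of mL, which nobody has argued matter clinically. All of this stands. It is why the grades should stay as a severity table and why the point is minor.

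Three stronger readings are tempting, and the documents do not support them:
- **That the volume is thrown away.** The text speaks of recording as well as grading, and the case report forms are not in the documents. The mL value may already be captured. What can be said is that no analysis of it is planned.
- **That a definite number of power points is lost.** No distribution, effect size or test is stated. The ranges above reflect the assumed medians, spreads and shifts, and other choices give other ranges.
- **That a trial conclusion is undermined.** Blood loss is not a primary, secondary, tertiary or listed exploratory outcome, and no power is claimed for it.

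Nor would mL make a null result strong. At 80% power the detectable difference is still about 0.50 SD with 40 vs 160 and 0.70 SD with 20 vs 80. The gain is that an estimate with a confidence interval shows which differences remain possible, and this serves clinical judgment better than a three-row table.

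**Conclusion.** The point holds as a low-cost improvement to a minor safety check. The three grades are the only scale on which Section 9.3 relates blood loss to nerve block group, and comparing grades alone is less sensitive than comparing the volumes behind them. That direction holds throughout the settings tried, but the size is conditional. Under the log-normal assumptions and a shift set at 80% power, the loss is about 7 to 55 points if controls bleed more and about 6 to 78 points if the four-drug arm does, which is the direction a check on added drugs should care about. It is largest when nearly all patients fall below 500 mL, and it can drop under 5 points for larger shifts. The simulations treat patients as one homogeneous population, so they do not model differences between knee and hip operations.

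**What to change.** Amend the sentence in Section 9.3, or add a line to Section 5.2, along these lines: estimated blood loss is recorded in mL; it is compared between nerve block groups on the mL or log-mL scale, stratified by TKA/THA, with the difference and its 95% CI; the three grades are tabulated by group as a descriptive severity summary.

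The cost is one sentence and, if the volume is not already captured, one numeric field on the case report form. No visit, procedure or patient is added, and the grades remain available. For patients already enrolled with only a grade on the form, the mL value would have to be taken from the operative or anesthesia record where it exists. The number without one should be reported.
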